10.3.6. Reporting of SAEs

SAE Reporting to Study Supporter via an Electronic Data Collection Tool

 • The primary mechanism for reporting an SAE to Study Supporter will be the electronic data collection tool (i.e., MedWatch 3500 form or Oncore SAE form) in accordance with Moffitt

SAE Reporting to Study Support via an Electronic Data Collection Tool

Cancer Center local regulations. The site will enter the SAE data into the electronic system as soon as it becomes available.

- After the study is completed at a given site, the electronic data collection tool will be taken off-line to prevent the entry of new data or changes to existing data.
- If a site receives a report of a new SAE from a study subject or receives updated data on a previously reported SAE after the electronic data collection tool has been taken off-line, then the site can report this information on a paper SAE form (see next section) or to the principal investigator by telephone.
- OncoSec Contacts for SAE reporting:

Oncosec Medical Representative:

[name]

Email: [contact]

10.4. Appendix 4: Contraceptive Guidance and Collection of Pregnancy Information

Definitions:

Woman of Childbearing Potential (WOCBP)

A woman is considered fertile following menarche and until becoming post-menopausal unless permanently sterile (see below).

If fertility is unclear (e.g., amenorrhea in adolescents or athletes) and a menstrual cycle cannot be confirmed before first dose of study intervention, additional evaluation should be considered.

Women in the following categories are not considered WOCBP

1. Premenarchal
2. Premenopausal female with 1 of the following:
 - Documented hysterectomy
 - Documented bilateral salpingectomy
 - Documented bilateral oophorectomy

For individuals with permanent infertility due to an alternate medical cause other than the above, (e.g., Mullerian agenesis, androgen insensitivity), investigator discretion should be applied to determining study entry.

Note: Documentation can come from the site personnel's: review of the subject's medical records, medical examination, or medical history interview.

3. Postmenopausal female
 - A postmenopausal state is defined as no menses for 12 months without an alternative medical cause.
 - A high follicle stimulating hormone (FSH) level in the postmenopausal range may be used to confirm a postmenopausal state in women not using hormonal contraception or hormonal replacement therapy (HRT). However, in the absence of 12 months of amenorrhea, confirmation with more than one FSH measurement is required.
 - Females on HRT and whose menopausal status is in doubt will be required to use one of the non-estrogen hormonal highly effective contraception methods if they wish to continue their HRT during the study. Otherwise, they must discontinue HRT to allow confirmation of postmenopausal status before study enrollment.

Contraception Guidance:

Acceptable methods include hormonal contraception (oral contraceptives – as long as on stable dose, patch, implant, and injection), intrauterine devices, or double barrier methods (e.g. vaginal diaphragm/ vaginal sponge plus condom, or condom plus spermicidal jelly), sexual abstinence or

a vasectomized partner. Abstinence is acceptable if this is the usual lifestyle and preferred contraception for the subject.

Collection of Pregnancy Information

Male subjects with partners who become pregnant

- The investigator will attempt to collect pregnancy information on any male subject's female partner who becomes pregnant while the male subject is in this study.
- After obtaining the necessary signed ICF from the pregnant female partner directly, the investigator will record pregnancy information on the appropriate form and submit it to the Sponsor-investigator within 24 hours of learning of the partner's pregnancy. The Sponsor will attempt to follow the female partner to determine the outcome of the pregnancy. Information on the status of the mother and child will be forwarded to the Sponsor. The Sponsor will follow the female partner until birth or termination of pregnancy when possible. Any termination of the pregnancy will be reported regardless of fetal status (presence or absence of anomalies) or indication for the procedure.

Female Subjects who become pregnant

- The investigator will collect pregnancy information on any female subject who becomes pregnant while participating in this study. Information will be recorded on the appropriate form and submitted to the Sponsor within 24 hours of learning of a subject's pregnancy.
- The subject will be followed to determine the outcome of the pregnancy. The investigator will collect follow-up information on the subject and the neonate and the information will be forwarded to the Sponsor. The subject will be followed until birth or termination of pregnancy. Any termination of pregnancy will be reported, regardless of fetal status (presence or absence of anomalies) or indication for the procedure.
- While pregnancy itself is not considered to be an AE or SAE, any pregnancy complication or elective termination of a pregnancy will be reported as an AE or SAE. A spontaneous abortion is always considered to be an SAE and will be reported as such. Any post-study pregnancy related SAE considered reasonably related to the study intervention by the investigator will be reported to the Sponsor as described in Section 8.3.4. While the investigator is not obligated to actively seek this information in former study subjects, he or she may learn of an SAE through spontaneous reporting.
- Any female subject who becomes pregnant while participating in the study will discontinue study intervention or be withdrawn from the study.

10.5: Collection of Human Samples for Immune Monitoring

Immune Monitoring tumor biopsies (fixed and fresh) as well as blood and fecal samples will be collected during this study to characterize the tumor microenvironment and to assess the immune phenotype and function pre- and post-combination therapy of tavo-EP and nivolumab.

Eligible subjects at all participating sites will take part in this immune monitoring. Fresh tumor biopsies will be collected at North America sites only. Biopsies should not proceed if (a) tumor is inaccessible or (b) biopsy is not thought to be in the subject's best interest, (c) the tumor is a target lesion and the biopsy is being collected between C1D1 and definitive surgery, or (d) non-target lesion (unless there is no change in LD and >15% of tumor volume). Biopsies do not need to be done if either the site investigator or person performing the biopsy judges that no tumor is accessible for biopsy that meet the size/volume requirements or that biopsy poses too great of a risk to the subject and will not be noted as a deviation. (If the only tumor accessible for biopsy is also the only lesion that can be used for RECIST v1.1 response evaluation, then the subject may be exempt from biopsy after discussion with the principal investigator and no deviation is documented). Other minor deviations will be recorded for subjects with procedures not done.

The samples will be collected during the study as specified in the SoA and shipped to the central laboratory, for storage, or to OncoSec or third-party vendors for analyses (including but not limited to immune-based assays, protein biomarkers and gene expression profiling, and RNA-seq).

Sample collection methods and handling at the study site are described below for each type of sample.

Tumor Biopsies

In addition to fixed biopsies, fresh biopsies are to be collected as specified in the SoA. Thus two tumor biopsies will be acquired from any accessible treated RECIST v1.1 measurable or non-target lesions >10 mm and/or untreated cutaneous lesions >5 mm. These biopsies will be placed into a shipping media ("fresh") and fixed in 10% formalin. Possible use include but is not limited to the following: Assess PD-L1 and immune marker levels in the tumor microenvironment (tumor, stroma and immune infiltrate) by chromogenic and multispectral immunohistochemistry (IHC) workflows. DNA and RNA may also be extracted from these fixed tumor biopsies and used to interrogate intratumoral gene expression by NanoString, RNA-seq analysis as well as epigenetic analysis with an Illumina Methylation Array workflow. The DNA from the biopsy may be used to detect levels of pIL-12 by qPCR, changes in clonality or antigen-specific TCR sequences with an Adaptive Biotechnologies analysis and the potential mutation load and neo-antigen repertoire in the tumor by whole exome sequencing. The fresh biopsy may be used in a flow cytometric assay to determine the frequency of PD-1^{hi}CTLA-4^{hi} cells in the live CD45⁺CD3⁺CD8⁺ gate (Daud, 2016) or to establish and culture tumor and TIL lines that may be used in functional immune assays.

If reasonable for subject therapy, at least 1 distal, non-target lesion shall be left untreated with biopsies taken at timepoints before and after treatment as described above. If only one biopsy is possible, the sample should be a fixed biopsy. For collection of tumor biopsies, the lesion should be accessible and of an appropriate size. The biopsy should be done under sterile conditions with adequate tissue to be collected: one 5 mm punch, core, or excisional biopsy. Prior to biopsy

Collection and if considered clinically indicated, coagulation assessment will be done including prothrombin time (PT), partial thromboplastin time (PTT), and international normalized ratio (INR).

Handling instructions for tissue biopsy are as follows:

Fixed Biopsy: A Fixed Tumor Biopsy Collection Kit should be used at all study time points for the collection of fixed tumor samples. Place the tumor tissue sample in the formalin container and close the cap tightly. After 12-24 hours, the tissue shall be placed in PBS (+ 0.01% azide) and stored at ambient temperatures until shipment.

Fresh Biopsy: Insert the fresh tissue sample into a pre-chilled container with XVIVO-15 media and immediately place on ice. The sample must remain cold and on ice until ready for overnight 4°C shipment to the central laboratory.

NOTE: Existing FFPE tumor samples from previous and future (while on study) melanoma tumor biopsies should be requested if available and should be submitted for research purposes. Up to 20 unstained slides may be requested if available. Provision of less than 20 slides is acceptable based on availability. This applies primary melanoma tumor lesions and metastatic melanoma tumor lesions. These should be requested in addition to the protocol indicated research biopsies.

Blood Sampling

Blood collected from the subject as outlined in the SoA may be used to evaluate changes in the subject's peripheral immune cells and circulating levels of pIL-12 by qPCR. Peripheral blood mononuclear cells (PBMC) isolated with BD's CPT tube (see details below) may be used in flow cytometric and ELISpot workflows to interrogate immune phenotype, tetramer frequencies and immune function. Blood will be collected for serum isolation and analysis of protein signatures.

Please refer to 'Human Sampling for Immune Monitoring manual' for details on blood sampling collection. Briefly, blood sampling will be collected for immuno-assays at the same time of blood chemistry collections as follows:

1. One 2.5 mL PAXgene™ RNA Vacutainer Tube
2. One 2.5 mL PAXgene™ DNA Blood Collection Tube
3. Nine 8.0 mL Vacutainer CPT Tubes

Handling for item 3 above: the CPT Tube should be at room temperature (18-25°C) and centrifuged within two hours of blood collection for best results. The cells in the upper phase (the plasma above the gel barrier) are to be re-suspended by inverting the unopened CPT tube gently 5 to 10 times before proceeding with shipment of processed blood at 4°C. Samples should be shipped same day as collection.

4. One 3.0 mL Vacutainer Serum Tube, Increased Silica Act Clot Activator

Handling instructions for item 4 above: Allow for the blood to clot by leaving it undisturbed at room temperature for 30 minutes. Remove the clot by centrifuging at 1,300 x g for 10 minutes in a centrifuge. Serum will be aliquoted and frozen, then shipped (if necessary) frozen where they will be stored at -80C. Samples should be shipped same day as collection.

Fecal Sampling

Approximately 2 grams of fecal matter will be collected by the subject using Norgen Biotek's Stool Nucleic Acid Collection and Transport tubes. If the subject cannot provide this sample at the clinical site, a kit will be provided to go home with the subject. Samples can be stored at room temperature up to 72 hours until ambient shipment to the laboratory where they will be

stored at -80°C. These samples will subsequently be used for 16S rDNA and/or metagenome sequencing, allowing for the elucidation of microbial composition and genome structure.

Subjects will be instructed to:

Avoid any contact between the stool sample and urine.

- Pass stool directly onto the provided plastic wrap (if stool is loose, subjects will use a provided large clean container) placed under the seat of the toilet.
- Scoop stool sample from three sites using the spoon attached in the cap and place the stool into the tube until the liquid reaches the “Fill To This Line” (Do not over fill).
- Tighten the cap and shake gently until the stool is thoroughly mixed with the preservative before returning the tube to the clinician or placing the tube in the shipping envelope.
- Samples collected at home will be stored in a sealed shipping envelope at room temperature for up to 72 hours, while the courier service will be notified for next day pickup.

10.6. Appendix 6: Medical Device Incidents: Definition and Procedures for Recording, Evaluating, Follow-up, and Reporting

Definitions of a Medical Device Incident

The detection and documentation procedures described in this protocol apply to all Sponsor medical devices provided for use in the study (see Section 6.1.1) for the list of Sponsor medical devices).

Medical Device Incident Definition

- A medical device incident is any malfunction or deterioration in the characteristics and/or performance of a device as well as any inadequacy in the labeling or the instructions for use which, directly or indirectly, might lead to or might have led to the death of a subject/user/other person or to a serious deterioration in his/her state of health.
- Not all incidents lead to death or serious deterioration in health. The nonoccurrence of such a result might have been due to other fortunate circumstances or to the intervention of health care personnel.

It is sufficient that:

- An **incident** associated with a device happened.

AND

- The **incident** was such that, if it occurred again, might lead to death or a serious deterioration in health.

A serious deterioration in state of health can include any of the following:

- Life-threatening illness
- Permanent impairment of body function or permanent damage to body structure
- Condition necessitating medical or surgical intervention to prevent one of the above
- Fetal distress, fetal death, or any congenital abnormality or birth defects

Examples of Incidents

- A subject, user, caregiver, or healthcare professional is injured as a result of a medical device failure or its misuse.
- A subject's study intervention is interrupted or compromised by a medical device failure.
- A misdiagnosis due to medical device failure leads to inappropriate treatment.
- A subject's health deteriorates due to medical device failure.

Documenting Medical Device Incidents

Medical Device Incident Documenting

- Any medical device incident occurring during the study will be documented in the subject's medical records, in accordance with the investigator's normal clinical practice, and on the appropriate form of the eCRF.
- For incidents fulfilling the definition of an AE or an SAE, the appropriate AE/SAE CRF page will be completed as described in Appendix 3.
- The eCRF will be completed as thoroughly as possible and signed by the investigator before transmittal to the Sponsor or designee.
- It is very important that the investigator provides his/her assessment of causality (relationship to the medical device provided by the Sponsor) at the time of the initial AE or SAE report and describes any corrective or remedial actions taken to prevent recurrence of the incident.
- A remedial action is any action other than routine maintenance or servicing of a medical device where such action is necessary to prevent recurrence of an incident. This includes any amendment to the device design to prevent recurrence.

10.7. Summary of Response Evaluation Criteria for Solid Tumors (RECIST) and Immune RECIST (iRECIST)

NOTE: Response evaluation by RECIST is required per protocol and it is optional by iRECIST.

10.7.1. RECIST v1.1

Tumor response will be evaluated according to RECIST guidelines ([Therasse, 2000](#)) using tumor imaging (see [Section 10.7.3](#) for tumor imaging details).

Assessment by RECIST v1.1 will be done as specified in the SoA. If during the neoadjuvant phase, a treatment delay results in shifting cycles, imaging and tumor evaluation will be shifted accordingly. Lesions will be numbered identically for each visit as Target and non-target, new lesions (see definitions in [Table 8](#)).

In support of RECIST v1.1, when more than one accessible and measurable tumor is present at baseline, all lesions (those with the longest diameter(s)/ organ that are measurable in the physicians' discretion) up to 2 cutaneous lesions assessed by photography and up to 5 visceral or subcutaneous lesions (2 per organ), assessed by radiology, with a maximum of 7 lesions total should be identified as measurable representative Target Lesions. A target lesion may be a treated or untreated lesion.

An 'accessible lesion' is defined as a cutaneous or subcutaneous lesion that can be reached from the surface with the electroporation needle array (with depth of up to 1.5 cm from the surface). Measurable lesions include non-lymph node longest axis ≥ 10 mm (on CT, PET-CT, MRI, or calipers/rulers), non-lymph node longest axis ≥ 20 mm (on X-ray) and lymph node short axis ≥ 15 mm. All lesions will be indicated by pen and numbered before being photographed. This provides the baseline map of ALL accessible lesions with baseline defined as the period between signing the ICF and prior to completion of Cycle 1. Each lesion will be identified by a lesion number which must remain the same throughout the study. Measurable lesions that are target lesions must be measured by the site and data entered into electronic data capture (EDC).

Each subject will be assigned a response category ([Table 5](#)): complete response (CR), partial response (PR), stable disease (SD), progressive disease (PD).

Preoperative response rate (unconfirmed) will be assessed during the Neoadjuvant phase (preoperative, unconfirmed).

Table 5 Response Evaluation Criteria in Solid Tumors v1.1

RECIST v1.1 Response Criteria	Target Lesions	Non-Target Lesions
Complete Response (CR)¹	Disappearance of all target lesions, determined by two separate observations conducted not less than 4 weeks apart. Any pathological lymph nodes (whether target or non-target) must have reduction in short axis to <10 mm (the sum may not be "0" if there are target nodes). There can be no appearance of new lesions.	Disappearance of all non-target lesions and normalization of tumor marker level. All lymph nodes must be non-pathological in size (<10 mm short axis).
Partial Response (PR)¹	At least a 30% decrease in the sum of the longest diameter (LD) of target lesions, taking as reference the baseline sum LD. There can be no appearance of new lesions.	Non-target lesions must be non-PD.
Stable Disease (SD)	Neither sufficient shrinkage to qualify for PR nor sufficient increase to qualify for PD, taking as reference the smallest sum LD since the treatment started.	Persistence of one or more non-target lesion(s) and/or maintenance of tumor marker level above the normal limits.
Progressive Disease (PD)	At least a 20% increase in the sum of diameters of measured lesions taking as references the smallest sum of diameters recorded on study (including baseline) AND an absolute increase of ≥ 5 mm, or the appearance of one or more new lesions.	Appearance of one or more new lesions and/or unequivocal progression of existing non-target lesions.

¹ Subjects will meet the primary endpoint (BORR) if they attain a confirmed CR or PR over the 24 weeks with the combination treatment with a 4-week confirmatory scan per RECIST v1.1.

10.7.1.1. Evaluation of Overall Response with RECIST v1.1

The overall response recorded from the start of the treatment until disease progression/recurrence (taking as reference for progressive disease the smallest measurements recorded since the treatment started). The subject's best response assignment will depend on the achievement of both measurement and confirmation criteria ([Table 6](#)).

Table 6 Overall Response Definitions using RECIST v1.1

Target Lesions	Non-Target Lesions	New Lesions	Overall Response	Best Response for this Category Also Requires
CR	CR	No	CR	Normalization of tumor markers, tumor nodes <10 mm
CR	Non-CR/ Non-PD	No	PR	
CR	Not all evaluated	No	PR	
PR	Non-PD / No all evaluated	No	PR	
SD	Non-PD	No	SD	Documented at least once ≥ 4 weeks from baseline
Not all evaluated	Non-PD	No	NE	
PD	Any	Any	PD	
Any	PD*	Any	PD	
Any	Any	Yes	PD	

* In exceptional circumstances, unequivocal progression in non-target lesions may be accepted as disease progression

Source: ([Seymour, 2017](#))

Other definitions

- Duration of response (DOR)
- Relapse free survival (RFS) – RFS is defined as the time, in months, from the first dosing date until the date of disease relapse (i.e., the date of the tumor imaging) or death from any cause. RECIST v1.1 will be used to determine the dates of relapse as this methodology is accepted by regulatory authorities. This will be further detailed in the SAP.
- Overall survival (OS) - OS is defined as the time from diagnosis until death from any cause. Subjects without a confirmed date of death will be censored at the last date when the subject was known to be alive.

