9.4.3. Efficacy Analyses

Endpoint	Statistical Analysis Methods
Primary	
Primary efficacy analyses will be performed on ASaT Population.
 
The pCR will be estimated based on the proportion of subjects with no viable tumor on histologic assessment at definitive surgery. The estimated pCR will be accompanied by a 2-sided 95% exact binomial confidence interval (CI). Refer to statistical analysis plan (SAP) for detail.

Secondary	
DOR, PFS, iPFS, iBORR and OS (time to events endpoints) will be summarized descriptively using Kaplan-Meier methods. The censoring rules will be defined in the SAP. The ORR, BORR, and iBORR (categorical endpoints) will be summarized in a similar fashion as pCR. These will be assessed by Investigator based on Response Evaluation Criteria In Solid Tumors (RECIST) v1.1 at 12 weeks of Neoadjuvant phase (preoperative, unconfirmed). Refer to SAP for detail. Further, the risk of surgical delay (either due to toxicity and/or tumor progression) will be assessed. Surgery will be planned at about 12 weeks and any delays beyond the protocol allowed window will be monitored and reported.

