10.7.2. Immune-Related RECIST (iRECIST)

iRECIST will be used to assess a secondary endpoint (refer to [Section 3](#)) according to recently published consensus guidelines for iRECIST ([Seymour, 2017](#)).

Assessment by iRECIST will be done at 12-week intervals as specified in the SoA. Lesions will be numbered identically for each visit as Target and non-target, new lesions (see definitions in [Table 8](#)).

Immunotherapeutics may result in infiltration of immune cells leading to transient increase in the size in malignant lesions, or undetectable lesions becoming detectable. The criteria are identical to those of RECIST v1.1 in many respects but have been adapted to account for instances where an increase in tumor burden, or the appearance of new lesions, does not reflect true tumor progression.

Unlike RECIST v1.1, iRECIST requires the confirmation of progression and uses the terms iUPD (immune unconfirmed progression) and iCPD (immune confirmed progression).

For target lesions, iCR, iPR, and iSD can all be assigned after iUPD has been documented, if iCPD was not confirmed (Table 7). iUPD is defined by RECIST v1.1 criteria for progressive disease; iUPD can be assigned multiple times as long as iCPD is not confirmed at the next assessment. Progression is confirmed in the target lesion category if the next imaging assessment after iUPD (4–8 weeks later) confirms a further increase in sum of measures of target disease from iUPD, with an increase of at least 5 mm. However, the criteria for iCPD (after iUPD) are not considered to have been met if CR, PR, or SD criteria (compared with baseline and as defined by RECIST v1.1) are met at the next assessment after iUPD. The status is reset (unlike RECIST v1.1, in which any progression precludes later CR, PR, or SD). iCR, iPR, or iSD should then be assigned; and if no change is detected, then the timepoint response is iUPD.

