Target lesions	All measurable lesions up to a maximum of 7 lesions total (and a maximum of 2 lesions per organ) with 2 cutaneous lesions assessed by photography and up to 5 visceral or subcutaneous lesions assessed by radiology. Measurable lesions should be representative of all involved organs and should be identified as target lesions and recorded and measured at baseline. Target lesions will be selected based on their size (lesions with the LD) and their suitability for accurate repeated measurements (either by imaging techniques or clinically). At baseline, the sum of the LD for all target lesions will be calculated and reported as the baseline sum LD. The baseline sum LD will be used as reference by which to characterize the

	
objective tumor response. After baseline, a value should be provided on the CRF for all identified target lesions for each assessment, even if very small. If extremely small and faint lesions cannot be accurately measured but are deemed to be present, a default value of 5 mm may be used. If lesions are too small to measure and indeed are believed to be absent, a default value of 0 mm may be used.

Non-target lesions	
All other lesions (or sites of disease) including any measurable lesions over and above the 7 target lesions should be identified as non-target lesions and should also be recorded at baseline. It is possible to record multiple non-target lesions involving the same organ as a single item on the case record form (e.g. “multiple enlarged pelvic lymph nodes” or “multiple liver metastases”). Bone lesions may be measurable if ≥ 1 cm on MRI. Measurements of these lesions are not required, but the presence or absence of each will be noted throughout follow-up. It is recommended that bone lesions be followed closely by investigators by comments and measurements whenever possible for retrospective review. Measurements are not required but these lesions should be noted at baseline and should be followed as “present” or “absent”.

Source: [\(Seymour, 2017\)](#)

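### Response rules in Appendix 10.7 (confirmed, open past surgery) contradict the preoperative, unconfirmed rule in Sections 3, 9.4.3 and 10.7.1

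*Combined protocol and SAP*

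**What the plan says.** Two sets of rules stand in the protocol.

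**Preoperative and unconfirmed.** Section 3 defines ORR by investigator RECIST v1.1 at 12 weeks, before surgery and without confirmation. It lists iBORR as optional and gives it no time point. BORR is not in the Section 3 endpoint table; it enters in Section 9.4.3: "The ORR, BORR, and iBORR (categorical endpoints) will be summarized in a similar fashion as pCR", with assessment "at 12 weeks of Neoadjuvant phase (preoperative, unconfirmed". Section 10.7.1 also describes the response rate as preoperative and unconfirmed. SoA note 5 plans two RECIST reads: baseline, and one within two weeks before definitive surgery.

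**Confirmed, with a window that does not end at surgery.**
- Section 10.7.1.1: "The overall response recorded from the start of the treatment until disease progression/recurrence", and "The subject's best response assignment will depend on the achievement of both measurement and confirmation criteria".
- Table 5, CR for target lesions: "Disappearance of all target lesions, determined by two separate observations conducted not less than 4 weeks apart".
- Table 5 footnote: subjects meet the primary endpoint, named there as BORR, if they "attain a confirmed CR or PR over the 24 weeks with the combination treatment with a 4-week confirmatory scan per RECIST v1.1".
- Section 10.7.2: "Assessment by iRECIST will be done at 12-week intervals as specified in the SoA".

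On absent lesions, Table 8 says: "If lesions are too small to measure and indeed are believed to be absent, a default value of 0 mm may be used". It does not mention lesions removed by the surgeon.

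**The concern.** In a neoadjuvant trial the surgeon removes the target lesions. A response measure that stays open after that point can record their absence without showing that the drugs caused it. A response definition therefore has to close before resection, or say that resected lesions are not evaluable. Section 10.7.1.1 does neither, and its confirmation requirement calls for a second look that the planned reads cannot supply before surgery.

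At stake are the secondary response rates meant to stand beside pCR. An analyst following Section 9.4.3 and one following Appendix 10.7 could report different BORR and iBORR values from the same subjects, and the second analyst's values could include surgical clearance.

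**Working it through.** **The plan's own figures.** The documents give no expected ORR, BORR or iBORR, so there is no response-rate figure to reproduce. The only design calculation is for pCR (Section 9.2): stop at 2 or fewer of 22, succeed at 7 or more of 33, 10% against 30%. The probability of success is the sum over x = 3 to 22 of C(22,x) p^x (1−p)^(22−x) × P(Y ≥ 7−x), with Y binomial (11, p). It is 0.0409 at p = 0.10 and 0.9018 at p = 0.30, in line with the stated 0.05 ceiling and 90% power. This calculation uses histology at surgery and no RECIST reading, so the present point does not affect it.

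**When surgery falls.** Inputs are four-week cycles, nivolumab on Day 8, three neoadjuvant cycles, and surgery about 2 to 4 weeks after the last dose (Section 4.1).
- Last neoadjuvant nivolumab: 2 × 28 + 8 = study Day 64.
- Surgery: 64 + 14 = Day 78 to 64 + 28 = Day 92.
- Time since Day 1: 77/7 = 11.0 weeks to 91/7 = 13.0 weeks.

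**Whether confirmation fits before surgery.** The one post-baseline read is at most 2 weeks before surgery. A second observation at least 4 weeks later falls at least 4 − 2 = 2 weeks after surgery.

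**Whether the other windows fit.**
- iRECIST every 12 weeks puts the second read at week 24, which is 24 − 13 = 11 to 24 − 11 = 13 weeks after scheduled surgery.
- The footnote's 24 weeks of combination treatment is twice the planned combination phase (3 × 4 = 12 weeks).

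**What a post-surgical read would be scored as.** No text says.
- If a resected lesion is entered as 0 mm, later reads can supply the disappearance that Table 5 asks for.
- If it is treated as not evaluable, the planned reads can never confirm a CR.

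**RECIST and iRECIST differ in exposure.** Under Section 10.7.1.1 the window closes at progression, so preoperative RECIST progression blocks a later CR. Under Section 10.7.2 an unconfirmed progression can be reset at the next read and does not preclude iCR as best response. A subject with preoperative iUPD whose lesions are then excised is not clearly excluded from iCR.

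**Whether post-surgical images will exist.** Standard-of-care scans are captured every 3 months for 2 years after surgery (Section 4.1), and Section 8.1.2 allows adjuvant-phase assessments where feasible.

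**The case against.** The strongest reply is that the analysis section already decides the matter. Section 9.4.3 names all three response rates and places them before surgery without confirmation, while Appendix 10.7 is headed as a summary of general criteria. The only RECIST entry in the SoA after the preoperative read is conditional on progression, which cannot produce a CR. Section 8.1.2 shows that the authors knew the tumor would be gone. Followed literally, Section 9.4.3 lets no postoperative CR into an analysed rate. All of that stands, and it makes this an inconsistency to reconcile.

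It does not remove the conflict. No sentence says that Section 9.4.3 overrides the appendix. That section lists iBORR both among the Kaplan-Meier endpoints and among the categorical ones, and ties it to RECIST v1.1 although Section 3 defines it by iRECIST. A best response taken from a single unconfirmed read adds nothing to ORR, so an analyst wanting a distinct BORR would look to Section 10.7.1.1. Section 9.4 leaves the detail to a SAP still to be developed.

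A reader might infer more: that any clear scan after surgery counts as CR, so that BORR would approach the resection rate whatever the drugs did. If 28 to 30 of 33 subjects were resected and later clear, that would be 28/33 = 84.8% to 30/33 = 90.9%. The documents do not support this. They give no resection count. Table 5 needs two observations, and Table 6 also needs non-target CR and no new lesions. Preoperative RECIST progression closes the window. The 0 mm default is optional and concerns lesions too small to measure.

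**Conclusion.** The contradiction is real. Parts of Appendix 10.7 require confirmation and a window reaching past surgery; Sections 3, 9.4.3 and 10.7.1 specify a preoperative, unconfirmed assessment. On the scheduled timing (surgery at about week 11 to 13, one post-baseline preoperative RECIST read), the appendix rules can be met only with reads taken after resection, and those reads have no scoring rule. If the appendix were applied, BORR and iBORR could partly reflect resection.

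The size of the effect cannot be derived from the documents. It depends on how many subjects are resected, how resected lesions are scored and which rule the analyst follows. The timing assumes surgery is neither delayed for extra cycles nor brought forward, both of which the protocol allows.

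The consequence is limited to secondary, descriptive summaries, and iRECIST is optional. The pCR endpoint, the Simon decision rule and its error rates are untouched. The footnote naming BORR as the primary endpoint conflicts with Section 3 but does not change the primary analysis described in Section 9.4.3.

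**What to change.** Before database lock:

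1. In Section 10.7.1.1, state that best overall response, by RECIST v1.1 and by iRECIST, is the best unconfirmed response from first dose to the last assessment before the first definitive surgical procedure or, for a subject without surgery, to the 12-week assessment. State that later assessments serve only to date relapse. Naming the first procedure matters because Section 10.8 allows definitive surgery to be split.
2. Remove the confirmation requirement from Section 10.7.1.1 and from the CR row of Table 5 for this endpoint.
3. Delete the Table 5 footnote.
4. In Section 10.7.2, replace the 12-week interval with the preoperative time point.

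DOR is listed as a secondary endpoint without a definition and is exposed to the same problem, so it should be defined in the same edit.

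The cost is a few sentences and no new data. The SoA notes record that all patients have completed the neoadjuvant phase, so the change affects analysis rules only, and it aligns the appendix with the time point already in Section 9.4.3. The one small downside is that BORR will then largely coincide with ORR.
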